Assuming that approximately 5% of patients with *BRCA* wild type (*BCRA*wt) disease screened in the study will carry a qualifying genetic alteration in any of the 13 genes involved in the HRR pathway (excluding *BRCA1* and *BRCA2*), it is estimated that approximately 25 patients will be included in the HRRm cohort before the target number of 250 patients with *BRCA*m disease is reached.

Study period	Timeline
Estimated date of first patient enrolled	Q2 (Q3) 2015
Estimated date of last patient enrolled	Q3 2017
Estimated date of last patient completed**	Q3 2018

** Estimated date of 150th progression free survival (PFS) event among patients with *BRCA*m disease

Study phase nomenclature will depend upon local regulatory approval status of olaparib. Preregulatory approval status will define ORZORA a phase IIIb study and IV study prior or post regulatory approval accordingly. Importantly, these differences do not affect study methodology. However the potential need for local regulatory or other agency notification should be determined for individual countries.

Study design

This is a prospective, open-label, single arm, multi-centre study to assess the clinical effectiveness and safety of olaparib maintenance monotherapy and will be conducted in line with the European Union (EU) approved prescribing information and indication in patients with platinum sensitive relapsed *BRCA*-mutated (germline and/or somatic) high grade epithelial ovarian, fallopian tube, or primary peritoneal cancer who are in response (complete response or partial response) to platinum-based chemotherapy.

BRCA mutations are documented germline or somatic mutations in *BRCA1* or *BRCA2* that are predicted to be deleterious or suspected deleterious (known or predicted to be detrimental/lead to loss of function).

An additional, exploratory cohort of patients with *BRCA*-independent qualifying alterations in genes involved in the HRR pathway will be enrolled into the study (HRRm cohort). Qualifying genetic alterations are loss of function (LOF) mutations in any of the 13 genes other than *BRCA1* and *BRCA2* involved in the HRR pathway that are predicted to be deleterious or suspected deleterious. These 13 genes are: *ATM, BARD1, BRIP1, CDK12, CHEK1, CHEK2, FANCL, PALB2, PPP2R2A, RAD51B, RAD51C, RAD51D,* and *RAD54L.* The investigational clinical trial assay known as the Lynparza HRR Assay from CCI will be used for this testing.

Figure 1 Study Flow Chart

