1.1.7 Clinical experience

Clinical experience with olaparib is fully described in the current version of the olaparib IB and the Prescribing Information (Appendix G) as applicable depending on country specific marketing authorisation status.

1.2 **Research hypothesis**

Olaparib administered as monotherapy as a treatment in routine clinical practice in the maintenance setting in line with the approved indication in the European Union (EU) exhibits the level of clinical effectiveness, safety and tolerability that are consistent with those seen in controlled clinical trials to date within the olaparib clinical development programme in the same treatment setting. Patients with somatic *BRCA* deleterious or suspected deleterious mutated disease (s*BRCA*m) appear to have consistent outcomes with those reported previously

in patients with gBRCAm ovarian cancer. The capsule formulation is appropriate to use in this clinical setting in patients with BRCA mutated relapsed ovarian cancer who have a complete or partial response to platinum-based chemotherapy.

The exploratory HRRm cohort will assess olaparib activity among patients with ovarian cancer who carry LOF genetic alterations among 13 genes, other than *BRCA1* and *BRCA2* (i.e., *BRCA*-independent HRRm), involved in the HRR pathway, as identified on an archival tumour sample by the Lynparza HRR Assay (see Section 1.1.4).

1.3 **Rationale for study design and doses**

Based on the results of a pivotal phase II trial (D0810C00019), described in more detail above (Section 1.1.3), olaparib as the capsule formulation at a daily recommended dose of 400 mg twice daily (a total daily dose of 800 mg) has been approved in EU as monotherapy for the maintenance treatment of adult patients with platinum sensitive relapsed (PSR) *BRCA* mutated (germline and/or somatic) high grade epithelial ovarian, fallopian tube, or primary peritoneal cancer who are in response (complete response or partial response) to platinum-based chemotherapy.

AstraZeneca in cooperation with the European Network of Gynaecological Oncological Trial Groups (ENGOT) is also conducting currently a phase III trial (D0816C00002) to confirm the outcomes of olaparib as maintenance monotherapy in patients with PSR *BRCA* mutation positive ovarian cancer. The phase III confirmatory trial is being conducted with the new tablet formulation.

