3. PATIENT SELECTION, ENROLMENT, RESTRICTIONS, DISCONTINUATION AND WITHDRAWAL

Each patient should meet all of the inclusion and none of the exclusion criteria for this study. These are designed in line with the EU approved indication for patients carrying *BRCA* mutated ovarian cancer. Under no circumstances can there be exceptions to this rule.

Patients with unknown germline *BRCA* mutation status, or patients found to carry *gBRCA*wt disease, or patients previously identified as having *BRCA*m disease based on a tumour test (with unknown *gBRCA* mutation status or with previously identified *gBRCA*wt status) will be considered for screening.

Patients previously diagnosed with gBRCAm disease will not be included in this study.

Patients with unknown *BRCA* mutation status who are considered for inclusion in this trial should be identified early so that the appropriate *BRCA* mutation screening procedures can be put in place in a timely manner.

In order to optimise the screening of patients and potential timely treatment initiation with study drug, patients may start the screening procedure from the end of cycle 3 of their current chemotherapy, if they are responding to treatment in the opinion of the investigator.

BRCA mutation status will be determined or confirmed through central blood and tumour testing as outlined in Figure 2 (see also Section 5.7.6).

Exploratory HRRm patient cohort

Patients screened for the study with unknown *BRCA* status or with known *gBRCA* status, for whom an adequate archival tumour tissue sample is available, will be tested for qualifying HRR gene alterations, as defined in Section 1.1.4.

Patients found not to carry a *BRCA* mutation in their tumour (tumour *BRCA*wt), and with qualifying *BRCA*-independent HRR genetic alterations will be included in the study (HRRm cohort), and analysed as a separate exploratory cohort.

Patients previously identified as having *BRCA*m based on a tumour test will not be screened for HRR gene mutations.

*Undetermined: the central tumour BRCA testing was unable to determine the presence or absence of BRCA mutation.

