3.1 Inclusion criteria

Screening procedures described in Section 3 should be strictly complied with. For inclusion in the study patients should fulfil the following criteria:

- 1. Provision of informed consent prior to any study specific procedures
- 2. Age 18 years or over
- 3. Documented germline or somatic mutation in *BRCA1* or *BRCA2* genes that is predicted to be deleterious or suspected deleterious (known or predicted to be detrimental/lead to loss of function) [Genetic counselling for patients with germline BRCA mutations should be performed according to local regulations]

Or

Tumour *BRCA*wt status and documented qualifying mutation in any of 13 genes involved in the HRR pathway, excluding *BRCA1* and *BRCA2* (*ATM, BARD1, BRIP1, CDK12, CHEK1, CHEK2, FANCL, PALB2, PPP2R2A, RAD51B, RAD51C, RAD51D,* and *RAD54L*), identified by the Lynparza HRR Assay in archival tumour tissue (i.e., *BRCA*-independent HRRm)

- 4. Patients with platinum sensitive relapsed high grade epithelial ovarian cancers (including primary peritoneal and/or fallopian tube cancer):
 - Platinum sensitive disease is defined as disease progression ≥6 months after completion of their last dose of platinum based chemotherapy
- 5. Patients should have received at least 2 previous lines of platinum containing therapy prior to enrolment:
 - For the last chemotherapy course immediately prior to enrolment on the study, patients must be, in the opinion of the investigator, in response (partial or complete radiological response) and no evidence of a rising CA-125, following completion of this chemotherapy course.
- 6. Patients must have normal organ and bone marrow function measured within 28 days of enrolment, as defined below:
 - Haemoglobin \ge 10.0 g/dL with no blood transfusions in the past 28 days
 - Absolute neutrophil count (ANC) $\ge 1.5 \times 10^9/L$
 - Platelet count $\geq 100 \text{ x } 10^9/\text{L}$
- 7. Total bilirubin ≤ 1.5 x institutional upper limit of normal (ULN), Aspartate aminotransferase (AST) (Serum Glutamic Oxaloacetic Transaminase [SGOT]) / Alanine aminotransferase (ALT) (Serum Glutamic Pyruvate Transaminase [SGPT]) ≤ 2.5 x institutional ULN unless liver metastases are present in which case they must be ≤ 5x ULN
- 8. Creatinine clearance > 50 ml/min (calculated)
- 9. Patients must be postmenopausal or have evidence of non-childbearing status for women of childbearing potential.

Postmenopausal is defined as any of the following:

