4. CLINICAL PARTICULARS

4.1 Therapeutic indications

Lynparza is indicated as monotherapy for the maintenance treatment of adult patients with platinum-sensitive relapsed *BRCA*-mutated (germline and/or somatic) high grade serous epithelial ovarian, fallopian tube, or primary peritoneal cancer who are in response (complete response or partial response) to platinum-based chemotherapy.

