PAES: In order to further define the long term efficacy of olaparib in patients with platinum sensitive relapsed BRCA mutated high grade serous ovarian cancer, the MAH should submit the final Overall Survival (OS) analysis of study D0810C00019, a phase II randomised, double blind, multicentre study.	
The clinical study report should be submitted by:	June 2017
PAES: In order to further confirm the efficacy of olaparib in patients with platinum sensitive relapsed BRCA mutated high grade serous ovarian cancer, the MAH should submit the results of study D0816C00002, a phase III randomised double-blind placebo-controlled multicentre study.	
The clinical study report should be submitted by:	December 2018
PAES: In order to further define the efficacy of olaparib in patients with platinum sensitive relapsed somatic BRCA mutated high grade serous ovarian cancer, the MAH should conduct and submit the results of a phase IV, open label, single arm, non-randomised, multicentre study in patients with relapsed platinum sensitive ovarian cancer who are in complete or partial response following platinum based chemotherapy and who carry loss of function germline or somatic BRCA mutation(s).	
The clinical study report should be submitted by:	September 2018

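### The protocol says it follows the EU indication, but it states that indication as high grade epithelial and enrols on that basis, while the label in its own Appendix G says high grade serous epithelial

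*Protocol*

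**What the plan says.** The synopsis (study design) says the study "will be conducted in line with the European Union (EU) approved prescribing information and indication in patients with platinum sensitive relapsed" disease, and goes on to name high grade epithelial cancer. Section 1.3 states the approval itself as covering BRCA mutated ("germline and/or somatic) high grade epithelial ovarian, fallopian tube, or primary peritoneal cancer who are in response" to platinum. It adds that maintenance will start as the EU indication provides, and Section 1.4 rests its benefit-risk judgement partly on use within that indication.

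Section 3 says of the inclusion and exclusion criteria: "These are designed in line with the EU approved indication for patients carrying" BRCA mutated ovarian cancer. Criterion 4 in Section 3.1 then admits "Patients with platinum sensitive relapsed high grade epithelial ovarian cancers (including primary peritoneal and/or fallopian tube cancer").

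Appendix G, section 4.1, gives the indication as BRCA-mutated ("germline and/or somatic) high grade serous epithelial ovarian, fallopian tube, or primary peritoneal cancer who are in response" to platinum. In Annex II of the same appendix, one post-authorisation measure has this aim: "In order to further define the efficacy of olaparib in patients with platinum sensitive relapsed somatic BRCA mutated high grade serous ovarian cancer".

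**The concern.** Section 1.3 and Appendix G 4.1 are almost the same sentence. The word that restricts the population to serous histology is missing from the first. Other parts of the protocol rely on the shorter version: the statement that the criteria follow the label, the benefit-risk argument, and the Section 1.2 hypothesis that effectiveness in routine use, in line with the approved indication, is consistent with earlier controlled trials.

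If non-serous patients are enrolled, the co-primary PFS estimates (sBRCAm and all BRCAm) describe a wider population than the one the protocol says it is studying. A reader comparing them with the phase II result, which the label describes as a serous population, could not separate a difference in effectiveness from a difference in case mix unless the serous patients are also shown separately.

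**Working it through.** **1. The passages side by side**

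| Item | Protocol body | Appendix G |
|---|---|---|
| EU indication | Section 1.3: high grade epithelial | 4.1: high grade serous epithelial |
| Who is enrolled | Criterion 4: high grade epithelial | Indication is serous |
| Phase II trial population | Section 1.1.3: high grade epithelial | 5.1: high grade serous |
| Post-authorisation measure, aim | not discussed | Annex II: high grade serous |
| Post-authorisation measure, study to be run | not discussed | Annex II: relapsed platinum sensitive ovarian cancer, no histology limit |

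The broader wording recurs in the synopsis, Sections 1.1.3, 1.3 and 1.5, and criterion 4, so it is not a one-off slip or an extraction fault. Section 1.4 calls the phase II patients the same population as this study's. That agrees with Section 1.1.3 but not with the label's account of the same trial.

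**2. Planned events**

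150/250 = 60% and 30/50 = 60%. The plan's own figures agree and are not in dispute.

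**3. Possible size (assumptions only)**

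The documents give no non-serous share. Take p = 5%, 10% and 20% as an assumed range.

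- sBRCAm, 50 patients: serous = 50 × (1 − p) = 47.5, 45, 40. Events at 60% = 28.5, 27, 24, against 30 planned.
- BRCAm, 250 patients: serous = 250 × (1 − p) = 237.5, 225, 200. Events at 60% = 142.5, 135, 120, against 150 planned.

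For the pooled median, take exponential PFS with a median of 11.2 months (the planning value in Section 8.1) in serous patients and an assumed 8 months in the others. Solve (1 − p)·2^(−t/11.2) + p·2^(−t/8) = 0.5:

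- p = 5%: t = 11.0
- p = 10%: t = 10.8
- p = 20%: t = 10.4

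The shift is 0.2 to 0.8 months. As a stress case, replace 8 with 4.3 months, the placebo median in BRCA-mutated patients of the phase II trial (Section 1.1.3). This gives t = 10.7, 10.1 and 9.1.

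**4. Set against the precision of the estimate**

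Approximate 95% CI for an exponential median: 11.2 × exp(±1.96/√events).

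- 30 events: 7.8 to 16.0 months
- 150 events: 9.5 to 13.1 months

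Every pooled median under the 8-month assumption lies well inside both intervals. In the stress case only the 20% value (9.1) falls below the narrower interval. Nothing in the documents suggests that non-serous BRCAm patients do worse, so the direction of any shift is also unknown.

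**The case against.** Several points on the other side stand, and each limits what can be claimed.

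- **No exceptions.** A reader might infer that Section 3 promises exception-free agreement with the label. The sentence about exceptions more naturally refers to each patient meeting all the criteria. The claim of alignment is looser, though it is still contradicted.
- **The post-authorisation measure.** A reader might infer that a study of mixed histology cannot answer it. The serous wording is in the aim; the description of the study to be run sets no histology limit, so wider enrolment is not barred. The protocol body also does not name the study that discharges the measure; the link is inferred from the matching design.
- **The 11.2-month median.** It is used only to project when 30 and 150 events will occur. The analysis is descriptive (median and 95% CI), with no threshold or test against that figure, so a different case mix invalidates no planned inference.
- **The subgroup list.** Section 8.4.3 says that other baseline variables may be assessed, with details in the SAP, which is not at hand. The absence of histology from the list is not itself an error.
- **Age of the label.** Appendix G is dated 26 February 2015 and the protocol 22 July 2016. A later label cannot be excluded from these documents. Appendix G is still the label that this edition attaches and cites, so the inconsistency remains until one of the texts changes.

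None of this removes the conflict between Section 1.3 and Appendix G 4.1, or the gap between criterion 4 and the indication it is said to follow.

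**Conclusion.** The inconsistency is established from the text alone and needs no assumption. It is more than clerical, because the misstated indication supports the eligibility statement, the benefit-risk argument and the research hypothesis.

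Its numerical consequence is not established. The co-primary PFS estimates may include patients outside the cited indication, but how many, and whether their PFS differs, cannot be learned from the documents. On the illustrative assumptions the effect is small relative to the confidence interval, and only the most pessimistic combination tried moves the BRCAm median beyond it. It would therefore go too far to conclude that the estimates are biased by a known amount or cannot inform the approved indication. This should be put right, but it does not threaten the primary analysis. The exploratory HRRm cohort is openly outside the BRCA indication and is not part of this point.

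**What to change.** 1. Reconcile the synopsis, Sections 1.1.3, 1.3, 1.4 and 3, and inclusion criterion 4 with Appendix G sections 4.1 and 5.1, covering both the indication and the description of the phase II population. Which histology rule applies is for the sponsor to decide. If a later label is the intended reference, attach it.
2. If the wider criterion stays, say in Sections 1.3 and 3 that it is broader than the attached label, and amend the alignment statements to match.
3. In that case, add histology (serous versus other) to the Section 8.4.3 list. Report a descriptive PFS median and 95% CI for the high grade serous subset of the sBRCAm cohort and of the BRCAm cohort.

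The cost is wording plus one descriptive table per cohort, with no added patients. The serous subset will have somewhat fewer events than the full cohort (24 to 28.5 instead of 30 in sBRCAm under the assumed 5-20% share), so its interval will be slightly wider. The sponsor should confirm that histology is recorded in the eCRF; the protocol does not show that it is.

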2.2 Secondary objectives

Secondary Objective:	Outcome Measure:
To assess the real world clinical effectiveness of olaparib maintenance monotherapy in patients with BRCA m ovarian cancer and patients with sBRCA m ovarian cancer, by assessment of: a) overall survival (OS), b) time to investigator-assessed second progression (PFS2), or death.	a) Time to deathb) Time to second progression event or of death if this occurs before second progression event.
To assess the real word clinical effectiveness of olaparib maintenance monotherapy in patients with BRCA m ovarian cancer and patients with sBRCA m ovarian cancer, by assessment of a) time to first subsequent therapy or death (TFST), b) time to second subsequent therapy or death (TSST) and, c) time to olaparib discontinuation or death (TDT).	 a) Time to first subsequent treatment commencement or death if this occurs before commencement of first subsequent treatment b) Time to second subsequent treatment commencement or death if this occurs before commencement of second subsequent treatment c) Time to olaparib discontinuation or death if this occurs before discontinuation of olaparib maintenance therapy.

Secondary Objective:	Outcome Measure:
To assess and describe the quality of life (QoL) of patients with BRCA m ovarian cancer and patients with sBRCA m ovarian cancer.	Functional Assessment of Cancer Therapy-Ovarian (FACT-O), Functional Assessment of Chronic Illness Therapy (FACIT)-Fatigue, and ORZORA QoL Additional Items Questionnaire.
To describe patterns of routine clinical use of olaparib, the nature and patterns of adverse events (AEs) of nausea and vomiting and their impact on QoL in patients with BRCA m ovarian cancer and patients with sBRCA m ovarian cancer.	Safety summary tables, Functional Living Index- Emesis (FLIE) Questionnaire, and concomitant medication use.
To describe nausea/vomiting toxicity management patterns used in routine clinical practice.	

2.3 Safety objectives

Safety Objective:	Outcome Measure:
To assess the safety and tolerability of olaparib maintenance monotherapy in patients with BRCA m ovarian cancer and patients with sBRCA m ovarian cancer.	AEs/serious adverse events (SAEs)/AEs of special interest (AESI)

2.4 **Exploratory objectives**

Exploratory Objectives:	Outcome Measure:
To describe the longer term safety of olaparib monotherapy, including follow up for Myelodysplastic Syndrome (MDS)/ Acute Myeloid Leukaemia (AML)/ New primary malignancies.	Collection of long term adverse events, including MDS/AML or new primary malignancies
To correlate the incidence of side effects and QoL according to age and the presence of comorbidities.	Based on collected and summarised outcomes and comorbidities
To describe the clinical effectiveness of (response to) subsequent line of treatment and correlating it with the progression-free interval (PFI) (artificial prolongation of PFI through olaparib).	Description of maximum response to subsequent line of treatment
To describe the efficacy of olaparib according to the previous therapy, with or without bevacizumab, and according to the PFI (recurrence during or after the end of bevacizumab maintenance).	Based on collected and summarised outcomes
To describe the activity of olaparib according to the germline mutational status (BRCA1 vs BRCA2), and to the presence of family history (yes vs not).	Based on collected and summarised outcomes and family history
To describe the kinetic of CA-125 progression according to Gynecological Cancer InterGroup (GCIG) criteria and its correlation with disease progression by RECIST 1.1 guidelines during olaparib therapy.	Based on collected and summarised outcomes
Exploratory Objectives:	Outcome Measure:
--	--
To measure loss of heterozygosity (LOH) for the BRCA1 and BRCA2 genes in tumour samples and explore any potential association with efficacy.	Based on all available tumour samples collected and summarised outcomes.
 To describe the real world clinical effectiveness and safety of olaparib maintenance monotherapy in patients with BRCA-independent HRRm ovarian cancer, by the following: Investigator assessed PFS according to RECIST 1.1 OS Safety and tolerability. 	 a) Time from study enrolment to disease progression (assessed according to RECIST 1.1 guidelines) or death b) Time to death c) AEs, SAEs, AESI
Potential exploratory research into frequency, nature and predictive value of HRR gene mutations, including BRCA1 and BRCA2 , may be performed on the optional collected and stored tumour samples available at study entry or tumour biopsy samples collected during the course of the study.	
These could include studying resistance mechanisms to olaparib, future exploratory research into factors that may influence development of cancer and/or response to study treatment.	
To collect and store deoxyribonucleic acid (DNA) (according to each country's local and ethical procedures) for future exploratory research into genes/genetic variation that may influence response to study treatment and or susceptibility to disease (optional)*.	
To explore the feasibility of reliably measuring s BRCA m and HRRm from circulating tumour DNA (ctDNA)*	

* These exploratory analyses may not be reported in the clinical study report (CSR), if not they will be reported separately.

